**Aim 3:** Examine the other attributes of RE-AIM (reach, adoption, implementation, and maintenance) of the two interventions using mixed methods to inform rapid dissemination and long-term sustainability among overweight and obese Latino men.

**Exploratory Aim 3:** Among those randomized to HOMBRE, examine socio-demographic determinants of modality choice and compare intervention engagement and effectiveness according to modality to inform future dissemination.

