### 2.2.7.3 Evaluation for implementation and dissemination

To complement the focus on effectiveness in Aims 1 and 2, we will assess the potential for implementation and dissemination using the RE-AIM framework's reach, adoption, implementation, and maintenance domains (**Table 5**), as we have done in other studies via interviews with study staff, coach, participant, and primary care and community stakeholders. We will conduct a detailed evaluation of these RE-AIM domains with mixed methods to gain a nuanced understanding of why the intervention is (or is not) superior to the minimally intensity intervention control, whether high intervention fidelity is achieved, what barriers and enablers there are, how these may translate into future implementation and dissemination, and what modifications can maximize implementation success. All interviews will be recorded and transcribed. Transcriptions of interviews with Latino patients will be translated to English.

Table 5. Summary of quantitative and qualitative measures for the process evaluation		
	Example Questions, Data Sources, and Methods	
RE-AIM Domains	Quantitative	Qualitative
Reach of the intended target population	Patient survey & recruitment tracking data: percentage and characteristics (e.g., language preference, place of birth, years in the US) of participants compared with non-participants.	Interviews with study staff: Barriers enablers of recruitment, recruitment variability by demographics or other characteristics, strategies for addressing barriers, potential strategies to maximize reach.
Adoption by target staff or settings	Administrative data: Characteristics of participating clinics, percentage and characteristics of PCPs approached who participated (e.g., PCPs referring or approving patients for study screening).	Interviews with PCPs and clinic leadership: Barriers and enablers of clinic and provider participation, recommendations for reducing barriers and maximizing adoption.

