Implementation success during intervention delivery ( staff perspective )	Surveys of lifestyle coach: perceptions of (1) consistency of intervention procedures with available evidence, (2) intervention suitability for primary care, and (3) experience with the strategies facilitating intervention delivery based on the Promoting Action on Research Implementation in Health Services model. 	Interviews with lifestyle coach, PCPs, and clinic leadership: Barriers and enablers of delivering the intervention and differences across participating clinics, modifications to maximize implementation success?
Implementation success during intervention delivery ( patient perspective )	We will assess intervention participants' engagement and adherence by monitoring the number of group sessions attended, reasons for missed sessions, secure messaging and self-monitoring frequency, and adherence across participant subgroups.	Interviews with a random sample of participants: Relevance and acceptability of knowledge and skills, frequency of practicing intervention strategies, perceived benefits, problems encountered, cultural congruence, satisfaction with program format, materials, and coach performance?
Maintenance of intervention effects in individuals and settings over time	We will assess attrition and adverse events by participant characteristics and treatment condition.	Interviews with lifestyle coach, PCPs, and clinic leadership: Potential for integration into regular care and sustained, resources, policies, and care process redesigns needed to maximize sustainability.

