**Aim 3:** For quantitative data collected as part of the assessment testing the potential for future implementation and dissemination, we will use t-tests for continuous variables and chi-square tests for categorical variables. For qualitative data collected related to aim 3, we will use NVivo, a multifunctional software system, to help code and manage data from the interview transcripts. We will initially use the interview guide to organize and provide a starting list of codes related to the factors associated with participant's values and preferences related to weight, diet and physical activity which we will supplement with emergent codes to capture new factors that arise from the group discussion. Two project team members will independently code the transcripts. Discrepancies in initial coding will be solved by discussion between project team members. Based on these discussions, the raters will conduct a final code of the transcripts. The general categories of codes will relate to modality, presentation, messages or motivations for weight loss important to men. Intercooder agreement will be quantified and reported for each coding domain using Cohen's Kappa, which is calculated as follows:  $(\text{Observed agreement} - \text{Chance}) / (1 - \text{Chance})$ . If substantial intercooder disagreements exist, a third project team member will review the text in question to determine appropriate coding before finalizing the coding scheme.

The purpose of the exploratory aim 2 & 3 analyses are to identify hypotheses for future rigorous studies. This study was not designed to have sufficient power to test the outcomes in exploratory analyses. In this case, multiple comparisons corrections will not be necessary.

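### The coding frame stated for the Aim 3 interviews does not map to four of the five interview rows of Table 5, which ask staff, the coach, PCPs and clinic leaders about barriers, enablers and sustainability

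*Combined protocol and SAP*

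**What the plan says.** Section 2.1 gives Aim 3 as: "Examine the other attributes of RE-AIM (reach, adoption, implementation, and maintenance) of the two interventions using mixed methods". It is one of the three main aims and carries no stated hypothesis.

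Section 2.2.7.3 says that these domains will be assessed "via interviews with study staff, coach, participant, and primary care and community stakeholders", and that the interviews will be recorded and transcribed. Table 5 sets out example questions, sources and methods in five rows, each with a quantitative and a qualitative cell. The qualitative cells include:

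- Reach: "Interviews with study staff: Barriers enablers of recruitment"
- Adoption: "Interviews with PCPs and clinic leadership: Barriers and enablers of clinic and provider participation"
- Implementation, staff perspective: "Interviews with lifestyle coach, PCPs, and clinic leadership: Barriers and enablers of delivering the intervention and differences across participating clinics"
- Maintenance, asked of the coach, PCPs and clinic leadership: "Potential for integration into regular care and sustained, resources, policies, and care process redesigns needed to maximize sustainability"

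The remaining row, Implementation from the patient perspective, interviews a random sample of participants about relevance, acceptability, cultural fit and satisfaction with the programme.

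The Aim 3 paragraph of section 2.2.9.1 covers the analysis of all qualitative data for this aim. The interview guide supplies a starting list of codes, described as concerning participants' values and preferences about weight, eating and activity. To these are added "emergent codes to capture new factors that arise from the group discussion". The categories are then described: "The general categories of codes will relate to modality, presentation, messages or motivations for weight loss important to men". Two team members code independently, settle differences by discussion and make a final coding. Cohen's kappa is to be reported for each coding domain, with a third member called in if disagreement is substantial.

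**The concern.** The analysis paragraph reads as if written for a study of what men want from a weight-loss programme. Most of the interviews in Table 5 ask something else: why recruitment, uptake by clinics and PCPs, delivery and continuation succeed or fail. The paragraph names no RE-AIM domain, no barrier or enabler, and no respondent other than the participant. Its group discussion is not among the sources listed in section 2.2.7.3 or Table 5.

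What is at stake is the qualitative half of a main aim. The final Discussion section relies on the mixed-methods data to inform implementation in real-world settings. If coders apply the stated frame, the views of the coach, PCPs and clinic leaders have no prespecified place in the results, and inter-coder agreement would be reported on domains other than those of Aim 3.

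**Working it through.** No arithmetic applies. The check compares the stated coding frame with the qualitative column of Table 5, row by row.

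| Table 5 row | Who is interviewed | Topic | Match with the stated categories |
|---|---|---|---|
| Reach | Study staff | Obstacles and aids to recruitment, ways to widen reach | None |
| Adoption | PCPs, clinic leadership | Obstacles and aids to taking part | None |
| Implementation, staff | Coach, PCPs, clinic leadership | Obstacles and aids to delivery, clinic differences, modifications | None |
| Implementation, patient | Random sample of participants | Relevance, acceptability, satisfaction with format and materials | Partial: format and materials overlap with modality and presentation |
| Maintenance | Coach, PCPs, clinic leadership | Integration into routine care, resources, policies, redesign | None |

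Count: 4 of 5 rows have no matching category and 1 of 5 has a partial match.

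**Who the frame is about.** The starting codes concern the participant, and the categories are limited to what matters to men. Both point to patient transcripts. The paragraph nevertheless introduces itself as the method for the Aim 3 qualitative data in general, and no other paragraph covers the staff, coach, PCP or leadership transcripts.

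**The group discussion.** The small-group discussions in section 2.2.4 are orientation activities, and no section lists them as an Aim 3 data source. Either the term in section 2.2.9.1 is a slip for interviews, or a source is missing from Table 5.

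**What the quantitative column covers.** Every row has a quantitative measure, and section 2.2.9.1 analyses these separately with t-tests and chi-square tests. They do not replace all of the interview content. For Maintenance the quantitative cell holds attrition and adverse events, which say nothing about continuation in clinics. For staff-perspective Implementation it holds surveys of the coach, so the views of PCPs and clinic leaders on delivery come only from interviews.

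**Order of the kappa step.** The paragraph runs: independent coding, discussion of differences, final coding, kappa, third member if needed before the scheme is finalised. It does not say which coding enters kappa. Sentence order suggests the final one. The third-member step suggests that agreement is assessed earlier. The text does not settle it.

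**The case against.** The strongest reply is that the frame is a starting point, not a closed list. The interview guide supplies the starting codes, and the guide is not in the documents; if it follows Table 5, it would bring in barriers, enablers and sustainability. Emergent codes are allowed, nothing says that the categories are exhaustive, and Table 5 presents its content as examples. A coach talking about delivery could also raise modality or messages.

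This stands in part. RE-AIM content could still be coded. But the paragraph itself describes the guide's starting codes as participants' values and preferences, and it names general categories that fit one row at best. Leaving four of five rows to codes that may or may not emerge does not show how those transcripts will be analysed.

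A reader might infer that Aim 3 would go unanswered. The documents do not support that. Aim 3 is mixed-methods, each row has a separately analysed quantitative measure, and the participant interviews are partly covered. A reader might also infer that Table 5 rules out group formats. It says only that there will be interviews, without saying that they are one to one; the point is that no group discussion is listed as a source.

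On kappa, a reader might infer that it is certain to measure agreement after consensus, and so to be inflated. That rests on sentence order alone, and the documents give no agreement rates from which to put a size on it. Only the lack of clarity stands.

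**Conclusion.** The concern holds for the qualitative part of Aim 3. The stated frame conflicts with sections 2.1 and 2.2.7.3: it matches none of the four rows that interview study staff, the coach, PCPs or clinic leaders, and partly matches the participant row. Followed as written, it would place those four rows' transcripts under categories that do not address reach, adoption, staff-perspective implementation or maintenance, apart from what the guide or emergent codes add.

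This rests on two assumptions: that the Aim 3 paragraph is the whole qualitative plan, and that the unseen interview guide is as that paragraph describes it. A guide built on the Table 5 topics would lessen the practical effect, though the text would still need correcting.

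The consequence is limited. The quantitative part of Aim 3, the primary outcome, the sample size and the error rates are not touched. The change is worth making because the interviews are the only planned source for some of the content, and the repair costs little.

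**What to change.** In the Aim 3 paragraph of section 2.2.9.1:

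1. Set the parent codes by RE-AIM domain (reach, adoption, implementation, maintenance) and by respondent type (study staff, coach, PCP, clinic leader, participant), with the Table 5 topics beneath them: barriers, enablers, modifications, resources and sustainability. Emergent codes can stay.
2. Keep the preference and motivation codes for the participant interviews.
3. Reconcile the group discussion with Table 5: change it to interviews, or add the discussion to Table 5 as a data source with its respondents and topics.
4. State that kappa is computed on the two independent first codings, before differences are discussed, and reported for the revised domains.

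The cost is rewording one paragraph before coding starts, with no new data collection. The reported kappa may be lower than one computed after discussion.

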#### 2.2.10 Sample Size and Data interpretation

This trial is powered on the primary outcome of percentage of participants achieving  $\geq 5\%$  weight loss at 18 months. A sample of 212 participants/arm has 80% power to detect a difference of 15 percentage points between the HOMBRE intervention and control at  $\alpha=0.05$  (2-sided), assuming at least 80% retention at 18 months based on our prior trial experiences. We estimated that the percentage of men randomized to the minimal intensity intervention who would maintain clinically significant weight loss at 18 months would be slightly lower than what we observed in a prior trial (39%). Among racial/ethnic minorities, such as Latinos, lower proportions have maintained clinically significant weight loss in the intervention arms (e.g., 18% to 26%). Additionally, other low intensity interventions in primary care have also demonstrated a lower proportion maintaining clinically significant weight loss than what was observed in a prior trial. We chose a 15-point difference in percentage of men achieving  $\geq 5\%$  weight loss at 18 months based on our prior studies and other available literature. Among men randomized to the coach-led intervention in a prior trial, 51% maintained  $\geq 5\%$  weight loss at 24 months (12-point difference between groups). We anticipate a greater difference than observed in our prior trial, given that HOMBRE incorporates facilitated choice or delivery options and the control condition does not. The SHED-IT intervention tested a lower intensity intervention with a higher intensity intervention among Australian men over 12 months and found that 33% and 49% of men randomized to the respective arms maintained clinically significant weight loss (16 point difference).

#### 2.2.11 Data Management and Quality Control

All study data will be entered into computerized data files utilizing: (1) Microsoft ACCESS for data entry on recruitment, follow-up, and intervention tracking; (2) WorldApp hosted at PAMF for self- and interviewer-administered questionnaire data and physical measurements; (3) the Nutrition Data System for Research (NDS-R) (Minneapolis, MN) licensed for data collection and nutrient analysis based on multiple-pass 24-hour diet recalls; and (4) a custom-designed web application for seven-day physical activity recall. WorldApp provides convenient multi-lingual functionality that allows participants to easily choose their preferred language for data collection. All data entry systems employ automatic, real-time range, logic, and missing value

checks. Also, the outcome assessors are trained on data collection protocols (e.g., multiple-pass 24-hour diet recall using NDS-R and 7-day physical activity recall), and their performance will be continuously monitored. Data sets will be cleaned, verified and archived, and then placed into SAS (version 9.2, SAS Institute, Cary, NC) data sets, which also will be archived. One official copy of all study data and a master data dictionary will be maintained and updated regularly by the study data analyst. All analytic and tracking databases will be stored in a password-protected, encrypted network drive with continuous backups. For the protection of participant confidentiality, unique anonymous study IDs will be used for data storing, tracking and reporting. Protected health information will be stored separately from all other study data, and used and disclosed in accordance with the Health Insurance Portability and Accountability Act regulations. Regular reports will be produced on (1) patient accrual and follow-up completion/retention in relation to goals and timeline; (2) the randomization process and group comparability on the balancing variables; (3) key baseline characteristics of the sample, by (blinded) group, related to the primary and secondary outcome variables and proposed effect modifiers and mediators; (4) intervention exposure and adherence; and (5) protocol violations. Any observed delays in these processes or data irregularities will be resolved in a timely manner.

#### 4. Discussion

Together with patients and other key stakeholders, such as healthcare providers, we designed a study to address the gap in evidence on how best to deliver behavioral lifestyle interventions to overweight and obese Latino men in primary care. The HOMBRE study is unique in that it tests a flexible and individualized package of delivery options for an evidence-based behavioral lifestyle intervention compared to a minimal intensity intervention in primary care over 18 months.

Using national data, we and others have reported that men in general and specifically Latino men are less likely to attempt weight loss or join weight loss programs than women. In a recent study, men were 60% less likely to attempt weight loss and 84% less likely to join a weight loss program compared to women. Similarly, among obese Latino adults, 42% of men reported attempting to lose weight compared to 61% of women. Diverse factors contribute to this disparity. Compared with women, men, including Latinos, more commonly misperceive themselves as normal weight when they are overweight/obese, and they experience less societal pressure for weight control. Rather, men's primary motivation for weight loss appears to be reducing chronic disease risk factors and avoiding adverse health outcomes - the emphasis of the GLB program. This is particularly true for midlife and older men with identified risk factors - the target population of the HOMBRE trial.

The primary care setting is ideal for capitalizing on this primary motivation for weight loss. However, there is limited research to inform primary care-based implementations. The participation of Latino men in behavioral lifestyle intervention trials based in primary care is difficult to quantify because ethnicity is not usually reported by sex. A systematic review documented only 546 Latino men (4%) among 15,356 participants in behavioral lifestyle intervention trials (not limited to primary care) where race/ethnicity was reported by sex. It is possible that men have not been the focus of primary care-based interventions because they utilize healthcare less often than women. While men may not use healthcare frequently, they still report a known usual place for medical care. Studies have shown that 86% of men age 45-64 years and 96% of men ≥65 years report a known usual place for medical care (excludes emergency room). Benefits of the primary care setting include potential for scalability given policy support for lifestyle interventions. The US Preventive Services Task Force recommends

referral to behavioral lifestyle interventions for obese individuals and for overweight individuals with 1 or more risk factors (diabetes, pre-diabetes, hypertension, dyslipidemia, and elevated waist circumference) encountered in primary care. Additionally, the Center for Medicaid Services reimbursement policies support implementation of behavioral lifestyle interventions in the context of primary care. In addition to policy support, implementation in primary care offers the benefit of leveraging PCP support for adoption and maintenance of behavior change.

The utilization of rapidly expanding health information technology modes of communication (e.g., Smartphone applications, Web-based applications, secure e-messaging) to provide culturally and linguistically appropriate weight management for high-risk Latino men in primary care is an important addition in this study. First, offering the option of videoconferencing is an innovative feature of the intervention that has not been evaluated with Latino men. We previously tested delivering a behavioral weight loss intervention in primary care to men only using Bluejeans videoconferencing (Blue Jeans™, Mountain View, CA). Obese men (BMI≥35 kg/m^2) randomized to the videoconferencing arm lost 3.5% (95% CI 2.1%, 4.9%) more weight than waitlisted controls. Second, HOMBRE incorporates technologies that enable self-monitoring including wearable activity monitors and Smartphone applications. Despite the evidence that internet and mobile phone interventions have shown promise for weight loss and maintenance in adults, few studies of DPP translations in Latinos have incorporated technology. Although Latinos have historically experienced the 'digital divide,' their access to technology in general and Smartphones in particular make this a promising approach to maximize reach in this population. The HOMBRE study will fill an important gap in the literature by integrating health information technology with traditional care models (e.g., group visits) to combat obesity among Latino men.

Testing a package of flexible delivery options as offered in HOMBRE presents a unique innovation in DPP translational research. It acknowledges a patients' desire for individualization and mirrors real-world applications where patients have choice in intervention programs. Very few studies have examined the potential benefits of this pragmatic approach. Kramer et al. showed that employees (n=89) randomized to an arm that offered 2 options for receiving the GLB (in-person groups or individual via videos) lost significantly more weight than those randomized to a non-choice, weight loss control arm (-10.4 lbs. or 5% vs. -2.3 lbs. or 1%, p<0.01) at 6-months. Piatt et al. tested 3 lifestyle intervention modalities (face-to-face groups, DVD, and internet education) among 555 adults and included one arm where participants could choose the delivery modality. Participants in the preference arm (n=101) lost 14.0 lbs. at 3 months and 8.7 lbs. at 6 months, which was significantly more than other groups at 3 months (p<0.03), but not at 6 months. The HOMBRE trial will build on this limited evidence by testing a package of flexible delivery options compared to a minimal intensity intervention whose effectiveness has been previously established.

Limitations of the HOMBRE trial relate to the pragmatic study design featuring in-person study visits at baseline and 18 months supplemented by follow-up data from the EHR over 24 months and a highly flexible intervention. Using the PRECIS (Pragmatic-Explanatory Continuum Indicator Summary) tool as a guide, the HOMBRE trial was designed to be pragmatic and yield evidence of the effectiveness of implementing an intensive lifestyle intervention in the context of routine primary care. As such, study design decisions favored pragmatic over explanatory methods. For example, while in-person follow-up visits extending to 24 months or longer is the gold standard for behavioral lifestyle trials, the HOMBRE trial aims to follow a large sample size (n=424) with lower patient burden, in part, by accessing weight data from the EHR. Other strategies to decrease patient burden include online self-administered questionnaires that can be completed at home and by phone between study visits. Additionally, the HOMBRE trial will

provide evidence of the effectiveness of a package of flexible delivery options and is not designed to compare the effectiveness of delivery options offered as part of the HOMBRE arm. The effectiveness of each delivery option compared to a usual care control has already been established. These pragmatic features of the HOMBRE trial will result in robust evidence of the effectiveness of an intensive lifestyle intervention for a group that has been underrepresented in diabetes prevention translational research.

Pragmatic studies, such as HOMBRE, that focus exclusively on high risk groups are critical for translating the benefits observed in tightly controlled efficacy trials such as the DPP into population-wide impacts on health disparities. Specifically, this study focuses on the priority population of Latino men who have been left out of diabetes prevention translational efforts to date, despite their high risk and significant population size. Furthering the benefit to address health disparities, the HOMBRE trial incorporates mixed methods to assess the potential for implementation and dissemination using the RE-AIM model. These data will supplement the comparative effectiveness trial outcomes by providing critical contextual information to inform implementation and dissemination in real world settings.

